3 OBJECTIVES AND ENDPOINTS

3.1 Objectives, Hypotheses, and Estimands

The study objective is to compare the safety and efficacy of BOTOX with placebo for the treatment of platysma prominence in adult subjects with moderate to severe platysma prominence at maximum contraction.

The clinical hypothesis is that BOTOX is a safe and effective treatment for the temporary improvement in the appearance associated with moderate to severe platysma prominence in adults.

Estimands: Primary Endpoints

The attributes of the estimands corresponding to the primary efficacy endpoints are summarized in [Table 1](#).

Table 1. Summary of the Estimand Attributes of the Primary Efficacy Endpoints

Attributes of the Estimand					
Estimand Label	Treatment	Variable (Endpoint)	Population	Handling of Intercurrent Events	Statistical Summary
Hypothetical estimand for primary endpoint	Single dose of BOTOX [REDACTED] or placebo	Composite achievement of a Grade 1 or 2 (Minimal or Mild) and at least a 2-grade improvement from baseline based on both investigator's assessment using the C-APPS and subject's self-assessment using the P-APPS at maximum contraction at Day 14	Intent-to-treat (ITT) (all randomized)	Subjects who discontinue study prior to Day 14 assessments or who do not have Day 14 C-APPS or P-APPS assessments will be included in the analysis as a hypothetical scenario in which the assessments were conducted as per protocol	Response rates and rate differences between BOTOX and placebo treatment groups; Cochran-Mantel-Haenszel (CMH) test [REDACTED]
Hypothetical estimand for coprimary endpoints	Single dose of BOTOX [REDACTED] or placebo	Achievement of at least a 2-grade improvement from baseline based on the following: 
• Investigator's assessment using C-APPS at maximum contraction at Day 14, and• Subject's self-assessment using P-APPS at maximum contraction at Day 14	Modified intent-to-treat (mITT) [REDACTED]	Subjects who discontinue study prior to Day 14 assessments or who do not have Day 14 C-APPS or P-APPS assessments will be included in the analysis as a hypothetical scenario in which the assessments were conducted as per protocol	Response rates and rate differences between BOTOX and placebo treatment groups; CMH test [REDACTED]

Estimands: Secondary Endpoints

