4 INVESTIGATIONAL PLAN

4.1 Overall Study Design and Plan

This is a 4-month, multicenter, randomized, double-blind, placebo-controlled Phase 3 study designed to assess the safety and efficacy of BOTOX treatment in adult subjects with moderate to severe platysma prominence.

To be eligible for enrollment, subjects must be at least 18 years of age, [REDACTED] and with either moderate (Grade 3) or severe (Grade 4) platysma prominence [REDACTED]

[figure not shown]
Eligible subjects will be randomized on Day 1 in a 1:1 ratio to receive BOTOX or placebo.

Approximately 400 subjects will be randomized at up to 35 global study sites.

Seven scheduled visits are planned: screening (Day -14 to Day -7), randomization/study drug (Day 1), follow-up visits (Days 14, 30, 60, 90), and study exit (Day 120). On Day 1, the study drug will be administered in the platysma muscle. Dosing will be determined based on the baseline C-APPS score on Day 1 (see Section 5.7).

The schematic of the study is shown in Figure 2.

Figure 2. Study Schematic

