7.3 Handling Potential Intercurrent Events for the Primary and Secondary Endpoints

The primary composite endpoint for the FDA and the coprimary endpoint for the EU regulatory agencies (defined in Section 3.2) will be analyzed based on the ITT population and the mITT population, respectively, and the following methods will be used to address potential intercurrent events:

- Subjects who did not receive any dose of study drug but are randomized will still be included in the ITT population. [REDACTED]
- Subjects who are randomized but prematurely discontinued the study before assessment of the primary endpoints will be considered as part of the ITT population. [REDACTED]
- Subjects who die before assessment of the primary endpoint will count as though they hypothetically continued in the study.
- Subjects who are lost to follow-up and are missing data for the primary endpoint will count as though they hypothetically continued in the study.
- Subjects who are missing assessments or data due to the COVID-19 pandemic and are missing data for the primary composite or coprimary endpoints will count as though they hypothetically continued in the study.
- Subjects who are missing data for any other reason for the primary endpoint will count as though they hypothetically continued in the study.

The efficacy analysis of secondary endpoints (defined in Section 3.3) will be analyzed based on the same populations as above with similar methods for addressing potential intercurrent events.

Missing values will be imputed per the below.

Missing data will be imputed using the following methods for the efficacy analyses:

- Multiple Imputation: The Multiple Imputation approach will be used as a primary analysis for the primary endpoint, as well as for all secondary endpoints. For the primary endpoint (US: composite endpoint; EU: coprimary endpoints) and the primary measure through Day 120. [REDACTED]

- Non-responder Imputation (NRI): The NRI analysis will categorize any subject who does not have evaluation during a specific visit window as a nonresponder for that visit. The NRI will be one of the sensitivity analysis approaches in the analyses of categorical variables for efficacy.

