7.4 Statistical Analyses for Efficacy

Summary and Analysis of the Primary Endpoints

Analysis of the primary endpoint will be conducted on the ITT population based on treatment as randomized for the US FDA analyses and on the mITT population based on treatment as randomized for the EU regulatory agencies.

US FDA: The composite responder endpoint for a Grade 1 or 2 (Minimal or Mild) and at least a 2-grade improvement will be analyzed using the CMH method [REDACTED]

EU regulatory agencies: In addition, the coprimary responder endpoints for at least a 2-grade improvement in the C-APPS and P-APPS separately will be analyzed using the CMH method [REDACTED]

The evaluation of the equality of the proportions of responders for the primary endpoint at Day 14 will be based on the CMH test stratified by baseline C-APPS score on Day 1 and by investigator site. A 2-sided p-value < 0.05 will be claimed as statistically significant. [REDACTED]

[REDACTED] The 95% CI for the treatment risk differences will be constructed using the normal approximation to the binary distribution.

Sensitivity analyses of the primary efficacy variables will be performed to establish their consistency and robustness as well as to further characterize the extent of subjects' responses. [REDACTED]

Summary and Analysis of Secondary Endpoints

Analysis of the secondary endpoints will be conducted on the ITT population based on treatment as randomized for the US FDA analyses and on the mITT population based on treatment as randomized for the EU regulatory agencies.

For the secondary endpoints, the proportion of responders will be analyzed using the CMH test [REDACTED]

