7.8 Sample Size Determination

Approximately 400 subjects will be randomized into the study in a 1:1 ratio yielding approximately 200 subjects in the BOTOX group and 200 subjects in the placebo group in the treatment period. [REDACTED]

[REDACTED]

[REDACTED]

For the US FDA primary analysis, an estimated sample size of 360 subjects will give a power of greater than 99% to detect a difference in responder rates between the BOTOX and placebo groups, assuming a 10% dropout rate by Day 14. [REDACTED]

[REDACTED]

[REDACTED]

The primary analysis for EU regulatory agencies only will be performed on the mITT population, [REDACTED]

[REDACTED]

a sample size of 180 will result in a power of greater than 99% to detect a difference between BOTOX and placebo in the proportion of subjects achieving at least a 2-grade improvement from baseline according to both investigator's assessment using C-APPS and subject's self-assessment using P-APPS at maximum contraction at Day 14. [REDACTED]

[REDACTED]

[REDACTED]

All calculations are based on a 2-sided Type I error rate of 0.05. The power calculation is based on a 2-sample test of independent proportions, as implemented in the commercial software nQuery version 7.0.

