2.3 Treatment Assignment and Blinding

Subjects will be randomized to BOTOX or placebo in a 1:1 ratio. Randomization will be stratified at each investigational site by baseline C-APPS on Day 1 [REDACTED]

[REDACTED] The same block will not be shared across sites or by baseline C-APPS.

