9.3.2 Main Analysis of Primary Efficacy Endpoints

The attributes of the estimands corresponding to the primary composite and coprimary efficacy endpoints for the US and EU regulatory agencies, respectively, are summarized in Table 1 (see Section 2.1).

Analysis of the primary endpoint will be conducted on the ITT population based on treatment as randomized for the US FDA analyses and on the mITT population based on treatment as randomized for the EU regulatory agencies.

US FDA: The primary responder composite endpoint for an achievement of Grade 1 or 2 (Minimal or Mild) and at least a 2-grade improvement in both C-APPS and P-APPS will be analyzed using the CMH method [REDACTED]

EU regulatory agencies: The coprimary responder endpoints for at least a 2-grade improvement in the C-APPS and P-APPS will be analyzed separately using the CMH method [REDACTED]

The evaluation of the equality of the proportions of responders for the primary endpoint at Day 14 will be based on the CMH test [REDACTED]

The 95% CI for the treatment

responder rate differences will be constructed using the normal approximation to the binomial distribution.

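### Does the confidence interval for the responder-rate difference need a stratified formula to match the stratified randomisation and CMH test?

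*Protocol*

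**What the plan says.** The two interval statements are nearly the same. Protocol 7.4: "The 95% CI for the treatment risk differences will be constructed using the normal approximation to the binary distribution". SAP 9.3.2: "responder rate differences will be constructed using the normal approximation to the binomial distribution". The Protocol's word for the distribution is a clerical slip for binomial.

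Stratification appears elsewhere. SAP 2.3: "Randomization will be stratified at each investigational site by baseline C-APPS on Day 1", with separate blocks for each site and grade. Protocol 7.4 bases the primary comparison on a "CMH test stratified by baseline C-APPS score on Day 1 and by investigator site". SAP 9.1 analyses a subject randomised in the wrong stratum by the actual stratum.

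The estimand table in Protocol 3.1 gives the population summary as "Response rates and rate differences between BOTOX and placebo treatment groups". For missing data, Protocol 7.3 says: "The Multiple Imputation approach will be used as a primary analysis for the primary endpoint, as well as for all secondary endpoints".

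Text is blacked out just before the interval sentence in Protocol 7.4, after the mention of the CMH test in SAP 9.3.2, in the statistical-summary cells of both estimand tables, and in the imputation paragraphs of Protocol 7.3 and SAP 9.2.

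**The concern.** The rate difference is the estimand's own summary measure, so its interval ought to be reproducible from the plan. As visible, a reader cannot tell whether the difference is crude or weighted over strata, which variance is used, or how results are combined over imputations.

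There is also a real statistical point. Stratified randomisation balances baseline grade between arms. The simple two-sample variance takes no credit for that balance and counts a difference in response between grades as noise. Grade could well be prognostic: a 2-grade improvement means reaching Grade 1 from Grade 3, but Grade 2 or better from Grade 4. The interval would then be wider than necessary and would not match the stratified test.

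At stake are precision and pre-specification of the interval. Type I error and the significance decision are not affected.

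**Working it through.** **The plan's own figures.** Protocol 7.8 gives 360 subjects "assuming a 10% dropout rate by Day 14". 360/(1 − 0.10) = 400, which reproduces. The power above 99% cannot be reproduced because the responder rates are redacted. With 180 per arm it needs a BOTOX rate of at least about 14% if placebo is 2%.

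**Assumptions for the check.** n = 200 per arm (Protocol 7.8). Mean response 40% on BOTOX and 2% on placebo in both grades, and a 50:50 grade split: all assumed, since none is visible. The gap g is the Grade 3 to Grade 4 difference in BOTOX response. Data are complete unless stated.

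**Three variances, with p₁ₛ and p₀ₛ the response rates in grade s:**

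- Wald: W = [p₁(1−p₁) + p₀(1−p₀)]/n = (0.24 + 0.0196)/200 = 0.001298. Half-width 1.96√W = 7.1 points.
- Within-stratum: V = mean over grades of [p₁ₛ(1−p₁ₛ) + p₀ₛ(1−p₀ₛ)]/n. This is valid if the grade mix is treated as fixed.
- Valid when the grade mix is random: V + B, where B = variance of the grade-specific differences/(2n) = (g/2)²/400.

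| Gap | V | B | √(V/W) | √((V+B)/W) |
|---|---|---|---|---|
| 0 | 0.001298 | 0 | 1.000 | 1.000 |
| 20 points | 0.001248 | 0.000025 | 0.981 | 0.990 |
| 40 points | 0.001098 | 0.000100 | 0.920 | 0.961 |
| 50 points | 0.000986 | 0.000156 | 0.871 | 0.938 |

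For the 40-point row the BOTOX rates are 20% and 60%, so V = [(0.16 + 0.24)/2 + 0.0196]/200 = 0.2196/200 = 0.001098. The excess W − (V + B) equals the between-grade variance of (p₁ₛ + p₀ₛ), divided by 2n. It is never negative, so the simple interval is never too narrow in large samples. It is exactly right when that sum is the same in both grades.

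**Simulation.** With 10% missing and multiple imputation by arm and grade (assumed), a fixed grade mix and a 40-point gap, the half-width went from 7.4 to 6.8 points. Wald coverage was 96.2% and within-stratum coverage 94.7%. With a random grade mix and complete data, within-stratum coverage fell to 94.0% at 40 points and 93.0% at 50. Adding B restored it to 95.2% and 94.7%, with width ratios of 0.960 and 0.937.

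**Dependence on the variance chosen.**

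- A grade-stratified Mantel-Haenszel difference with the Sato variance had width ratio 1.000 at every gap tested in the setting above.
- With 180 per arm, BOTOX 20%/60% and placebo 1%/5%, its width was 0.149 against 0.151 for Wald, about 1% narrower. In an extreme case (10%/70% and 0%/10%) it was 0.148 against 0.156, about 5% narrower.
- Full site-by-grade strata number up to 35 × 2 = 70, or 400/70 = 5.7 subjects each. With the Sato variance, that interval was 2% wider than Wald at 400 subjects and 10% wider at 180.

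**Effect on the decision.** At the assumed rates the difference is 0.38/√0.001298 = 10.5 standard errors from zero. CMH and Wald significance disagreed in 0% of simulated trials in every setting.

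**The case for a change.** The strongest case for a change is pre-specification. The SAP is meant to hold the full detail, yet its visible sentence adds nothing to the Protocol's. If the blacked-out text is silent too, the form of the interval for the headline estimate could be chosen after unblinding. The options differ: at 180 subjects and a 40-point gap they run from about 0.92 to 1.10 times the Wald width. Closing the gap would take a sentence or two.

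Part of this stands. The visible text does not fix the form of the interval, and the conservatism of a simple interval is real when grade is prognostic. Three things weaken the case.

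- The lower end of that range comes from the within-stratum variance, which is too small if the grade mix is random. The upper end comes from site-by-grade strata with the Sato variance. Neither is the natural reading of a sentence that names only a normal approximation.
- No rates by grade are visible, and the direction of any gap is open. Protocol 4.1 says: "Dosing will be determined based on the baseline C-APPS score on Day 1". The US composite also requires response on the P-APPS, which is not a named stratum.
- A grade-weighted difference would still not match the CMH test, which also stratifies by site. It would also differ slightly from simple subtraction of the tabulated rates: by 0.3 points on average, and 0.8 at the 95th percentile, at a 40-point gap with 400 subjects.

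One qualification goes the other way. With few subjects and low rates, the simple interval can fall slightly below nominal: 94.2% coverage at 180 subjects in total with BOTOX 12%/22% and placebo 0.5%/1.5%. The grade-stratified Mantel-Haenszel interval covered 94.1% in the same runs, so stratifying is no cure.

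**Conclusion.** The plan needs no change. The strata, weights, variance and pooling rule cannot be called absent, because the places where they would stand are blacked out and the visible wording fits a stratified interval as well as a simple one. A statistician with the full SAP can look this up.

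If the visible sentence is the whole rule, analysts would compute the normal-approximation interval in each imputed data set and combine by Rubin's rules. That interval is valid in large samples and at worst somewhat wide. Under the assumed 40% and 2% response rates, equal grade split and 200 per arm, the width that could validly be saved is about 1% at a 20-point gap, 4% at 40 and 6% at 50. Larger savings (8% at 40 points and 13% at 50 with complete data) require treating the grade mix as fixed. The CMH decision stays the same in every setting examined. The choice between a crude difference that matches the tabulated rates and a slightly tighter weighted one is a fair trade-off.

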7.5 Statistical Analyses for Safety

The safety analyses will be performed using the safety population. The safety parameters will include incidence of AEs and change from baseline in vital signs. [REDACTED]

Treatment-emergent AEs are defined as any AE with the onset that is after the first dose of study drug.

An overview of AEs will be presented consisting of the number and percentage of subjects experiencing at least one event for each of the following AE categories:

- Any TEAE
- Any TEAE related to study treatment according to the investigator
 - Any TEAE related to study procedure according to the investigator
 - Any TEAE related to study drug according to the investigator
- Any severe TEAE
- Any serious TEAE
- Any TEAE leading to death
- Any AESI

- Any PDSOT AE
- All deaths

Treatment-emergent AEs will be summarized by system organ class (SOC) and PT; by maximum relationship to study drug as assessed by the investigator (e.g., reasonable possibility or no reasonable possibility) and SOC and PT; by maximum severity and SOC and PT; and by subject number and SOC and PT. Specific TEAEs will be counted once for each subject for calculating percentages, unless stated otherwise. In addition, if the same AE occurs multiple times within a subject, the highest severity and level of relationship to investigational product will be reported.

Vital sign measurements will be summarized for changes from baseline at each assessment timepoint.

[figure not shown]
7.6 Interim Analysis

Interim analyses are not planned for this study.

7.7 Overall Type I Error Control

Analyses will be conducted using a gated hierarchical testing procedure to preserve a familywise Type I error rate of $\alpha = 0.05$.

To control the family-wise Type I error rate at 0.05 for multiplicity across the primary and secondary analyses, a hierarchical testing strategy ²³ will be used.

Nominal p-values will then be provided.

7.8 Sample Size Determination

Approximately 400 subjects will be randomized into the study in a 1:1 ratio yielding approximately 200 subjects in the BOTOX group and 200 subjects in the placebo group in the treatment period. [REDACTED]

[REDACTED]

[REDACTED]

For the US FDA primary analysis, an estimated sample size of 360 subjects will give a power of greater than 99% to detect a difference in responder rates between the BOTOX and placebo groups, assuming a 10% dropout rate by Day 14. [REDACTED]

[REDACTED]

[REDACTED]

The primary analysis for EU regulatory agencies only will be performed on the mITT population, [REDACTED]

[REDACTED]

a sample size of 180 will result in a power of greater than 99% to detect a difference between BOTOX and placebo in the proportion of subjects achieving at least a 2-grade improvement from baseline according to both investigator's assessment using C-APPS and subject's self-assessment using P-APPS at maximum contraction at Day 14. [REDACTED]

[REDACTED]

[REDACTED]

All calculations are based on a 2-sided Type I error rate of 0.05. The power calculation is based on a 2-sample test of independent proportions, as implemented in the commercial software nQuery version 7.0.

8 ETHICS

8.1 Independent Ethics Committee/Institutional Review Board

The protocol, Investigator Brochure, informed consent form(s), recruitment materials, and all subject materials will be submitted to the IEC/IRB for review and approval. Approval of both the protocol and the informed consent form(s) must be obtained before any subject is enrolled. Any amendment to the protocol will require review and approval by the IEC/IRB before the changes are implemented to the study. In addition, all changes to the consent form(s) will be IEC/IRB approved.

8.2 Ethical Conduct of the Study

The study will be conducted in accordance with the protocol, Operations Manual, International Council for Harmonisation of Technical Requirements for Pharmaceuticals for Human Use (ICH) guidelines, applicable regulations, and guidelines governing clinical study conduct and the ethical principles that have their origin in the Declaration of Helsinki. Responsibilities of the investigator are specified in [Appendix B](#). Investigators should notify AbbVie if any urgent safety measures are taken to protect the subjects against any immediate hazard.

8.3 Subject Confidentiality

For personal data that AbbVie controls and maintains, AbbVie has developed a robust security program to protect subject personal data focused on due diligence in design, managed change, and information security governance. Information security policies govern the information security functions including identity and access management, operations, infrastructure, application, and third-party security requirements. The risk-based AbbVie Data Classification Tool dictates the level of scrutiny and control required for the relevant activities per AbbVie's information security policies taking into account the sensitivity of the data.

Before subject data is shared with AbbVie, the study doctor and staff will replace any information that could directly identify a patient (such as name, address, and contact information) with a generic code which AbbVie cannot link to that subject's identity to protect the confidentiality of the data.

AbbVie has a data protection impact assessment (DPIA) program to ensure and document the appropriate controls and safeguards stated above are in place for clinical trial data that it controls and maintains, and these processing activities respect the privacy of clinical trial subjects. AbbVie also maintains robust security incident response policies and procedures, including requirements for the containment of any data related incidents, the mitigation measures where needed, and notification to authorities or affected individuals where required.

To protect subjects' confidentiality, all subjects and their associated images will be assigned numerical study identifiers or "codes." No identifiable information will be provided to AbbVie.

